The risk is also greater with smoking, obesity, premature postsurgery exercise, heavy lifting, recurrent vomiting, coughing, or an improper diet that leads to constipation.

Any wound dehiscence needs to be treated as a new wound and is a surgical emergency that requires immediate attention. Surgical debridements, antibiotic therapy, reclosure with the appropriate surgical technique, and sutures represent the most appropriate treatments. Finally, the patient's wound should be closely monitored to prevent dehiscence from recurring.

For all the above mentioned reasons, wound dehiscence always needs to be prevented as much as possible.

Therefore, a new, polyurethane-based topical skin adhesive has been developed: MAR-CUTIS. MAR-CUTIS is intended for topical application to close wounds of the skin, such as cuts and wounds from surgical incisions. It consists of a polyurethane-based prepolymer and an amino acid-based hardening agent which are provided in prefilled, double syringes with a mixing cannula and spreader tip.

Information about the preclinical testing as well as known and expected benefits, risks, serious adverse events (SAEs) and reasonably anticipated adverse events (AEs) of MAR-CUTIS are to be found in the Investigator's Brochure.

In particular, there are some predictable AEs (rates) that have been observed with other skin adhesives and can be possibly associated with the use of MAR-CUTIS:

- Infection (3.6%) after wound closure; this also applies to sutures and is not limited to adhesives.
- Dehiscence (2.5%) which is greater in wounds closed with skin adhesive as compared to other methods of wound closure (namely sutures, staples and strips).
- Improper application of the skin adhesive (unknown).

- Allergic reactions (11.5%).
- Other additional risks mentioned in risk management file, eg, pain (6.1%), edema (9.7%), and warmth (1.3%).

Such novel polyurethane-based medical adhesive differs from existing technologies due to its unique composition. The adhesive technology is:

- Fully Synthetic
- Easy to use
- Flexible

Based on polyurethane, it is completely different from existing skin adhesives based on cyanoacrylate. This new component is adhering to the tissue via mechanical and physical adhesion, forming a strong, yet flexible film. There is no reaction with the tissue itself; a strong polymer network is quickly formed and full polymerization is completed after a few minutes.

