### 7.4.5 Application in the Study

Detailed instruction and a training video on the application of MAR-CUTIS will be provided to each investigational site. MAR-CUTIS will be applied in one 1 to 2 mm thick layer, ensuring that at least 1 cm of the glue is applied over the length of the wound on each side.

---

The amount of the glue applied will be calculated such that one 5-mL syringe covers approximately 8 cm of wound length (giving a total of 10 cm per syringe). For wounds >8 cm, 2 syringes will be required. The wound will be held for approximately 30 seconds to allow for initial polymerization. Only for the pediatric population, the maximum number of syringes per day is limited based on the body weight as shown in the table below:

Body Weight	Number of MAR-CUTIS Syringes
10 to <15 kg	Maximum of 1 syringe
15 kg and above	Maximum of 2 syringes

Detailed instruction and a training video on Dermabond Advanced application will also be provided to each investigational site. Use of Dermabond Advanced will be according to Instructions for Use (Section 15.2). Dermabond Advanced will be applied in one continuous layer onto a dry wound through painting motions, taking care not to apply adhesive between the wound edges. Applying a second layer is not required or recommended. If a second layer of Dermabond Advanced is applied or if large droplets of liquid are not spread thinly, the subject may experience an increased sensation of heat or discomfort. The wound will be held for 60 seconds to allow for complete polymerization.

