##### **8.1.2 Baseline Visit (Day 0)**

Screening and baseline can occur on the same day. The following procedures will be performed at the Baseline Visit:

- Reassess for eligibility against the inclusion and exclusion criteria if baseline is not on the same day as screening.
- Record concomitant medication (Excluding related to intraoperative anesthesia).

- 
- Record adverse events.
  - Record of incidents and device performance, device-related complaints
  - Perform a urine beta-human chorionic gonadotropin ( $\beta$ -HCG) pregnancy test (in all female subjects of childbearing potential [post-menarchal and pre-menopausal]).
  - Issue a subject diary.
  - Subject-related questionnaire completed by investigator.
  - Evaluation of incision/laceration (incidence and grading).

When all the baseline procedures have been performed, subjects will be randomized (the 3 stratification factors of age group, wound type, and skin type will be recorded). All wounds, including those that require debridement and/or deep suturing, will be prepared for closure as per the standard of care at a treating hospital. The investigator will assess the need and perform closure of deep tissue layers as necessary before proceeding with the closure of the last (dermal) layer with the IMD. Once the IMD has been applied to the wound, the investigator will complete the specified portion of the subject-related questionnaire.

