#### Section 1 (to be completed at Day 0)

- |  |     |    |
|--|-----|----|
| 1) Application of the glue strip   |     |    |
| Easy   | Yes | No |
| Fast   | Yes | No |
| Without complications  | Yes | No |
| 2) Overall, would you say that the use of the glue saved you time as compared with the use of sutures? | Yes | No |
| 3) Overall, would you say that the use of the glue reduced effort?                                     | Yes | No |

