#### Section 2 (to be completed at Month 1)

##### Practical experience

- 8) Please rate your impression on the usability of this product on a scale from 1 (poor = very difficult to use) to 100 (excellent = very easy to use)

- 9) With regards to this subject, my experience with MAR-CUTIS can be described as
- Very satisfied
  - Satisfied
  - Dissatisfied
  - Very dissatisfied
- 10) Did you observe any pain or burning at time of application?
- Yes
  - No

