13.2.6 Medical practitioner overall satisfaction and ease of use with the Device

For the evaluation of the overall satisfaction of the medical practitioner with the Device during and after the closure of the target surgical incision/laceration two questionnaires will be applied:

- 1) Product-related questionnaire for Investigators, to be completed for each center when the last randomized subject at the center completes the D10 visit. The same questionnaire will be completed for both MAR-CUTIS and Dermabond.

This questionnaire consists of 8 yes/no questions and 1 opinion question that evaluate the investigator's experience with use of the adhesive (i.e., instructions easy to understand, preparation of the syringe being easy and fast, glue hardening time).

- 2) Subject-related questionnaire for Investigators, to be completed at the Day 0 and Month 1 visits, and recorded in the e-CRF.
 - The questionnaire for Day 0 consists of 5 yes/no questions that assess the investigator's experience applying the adhesive (i.e., easy to use, fast, without complications, time saving and reduced efforts).
 - The questionnaire for Month 1 consists of a visual analog scale that rates usability of the product from 1 to 100, and two questions that evaluate the experience with the adhesive and the pain or burning at the time of application. Moreover, it also contains additional questions to describe the event of a premature removal of the adhesive.

Descriptive statistics for each question of both questionnaires will be presented for the analysis of this endpoint.

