16.1.1.9 Conversion of time intervals

If a time interval was calculated in minutes, hours or days and needs to be converted into months or years, the following conversion factors will be used:

- 1 month = 30 days.
- 1 year = 365.25 days.

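### The investigator is asked about pain or burning at application at Month 1, some 23 to 37 days afterwards, although the same form has a section completed on Day 0

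*Protocol*

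**What the plan says.** Protocol 15.6 divides the subject-related questionnaire for investigators into three sections: one for Day 0, one for Month 1, and one used only if the adhesive is deliberately removed early. The Day 0 section asks whether application was easy, fast and free of complications, and whether the glue saved time and effort. The Month 1 section holds a usability scale, a satisfaction rating and item 10, answered yes or no: "Did you observe any pain or burning at time of application".

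SAP 13.2.6 confirms the placement. It describes the Month 1 part as a usability scale plus "two questions that evaluate the experience with the adhesive and the pain or burning at the time of application". Protocol 9.2 describes the same form but does not mention the pain item.

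On the Day 0 section, Protocol 8.1.2 says: "Once the IMD has been applied to the wound, the investigator will complete the specified portion of the subject-related questionnaire".

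The schedule in Protocol 7.1.2 gives Month 1 a window of 7 days either way. It also has the form completed at Early Discontinuation if that precedes Month 1 or if the form has not yet been completed. Protocol Section 6 lists the form as an endpoint for the objective on subject comfort during and after treatment.

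**The concern.** Pain or burning while an adhesive is applied is brief and best recorded at once. Here the question waits about a month, while a section of the same form is filled in on the day.

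Two problems follow. First, a mild, short-lived reaction is easily forgotten. Second, the study is open-label, and Protocol 7.4.7 itself accepts that endpoints other than dehiscence may be biased for that reason. At Month 1 the investigator also knows whether the wound healed well, and has just rated satisfaction in the preceding item. A Day 0 answer would still be unblinded, but it could not be coloured by the outcome.

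In addition, a subject who has neither a Month 1 nor an Early Discontinuation form contributes no answer about something that happened on Day 0.

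At stake is the part of the comfort objective that concerns the time of treatment itself, for which item 10 is the only specific question.

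**Working it through.** The plan gives no figure of its own on this point, so the check is the recall interval and a comparison of the instruments.

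**Recall interval**
- Length of a month: SAP 16.1.1.9 converts time intervals with "1 month = 30 days". I assume the nominal Month 1 visit follows the same rule.
- Visit window: 7 days either way (Protocol 7.1.2).
- Earliest: 30 − 7 = 23 days. Nominal: 30 days. Latest: 30 + 7 = 37 days.
- At an Early Discontinuation visit before Month 1 the interval can be shorter.
- With the item in Section 1, the answer would be given on the day of application.

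**Does another form ask the same question?**
- *Day 0 section of the same form (15.6).* It asks whether application was free of complications. A negative answer could reflect pain, but does not identify it.
- *Subject's Day 10 questionnaire (15.7).* It covers pain now and average pain over the last 7 days. The Day 10 window is 2 days either way, so the earliest visit is Day 10 − 2 = Day 8. Seven days back from there is 8 − 7 = Day 1, so Day 0 lies outside the recall period even at the earliest visit.
- *Subject's Month 1 questionnaire (15.7).* It covers current pain only.
- *Adverse events (9.3.2.1).* These are recorded from consent onwards and may be observed or volunteered, but questioning must stay general and must not prompt for particular symptoms.
- *Device performance (SAP 12.3).* It summarises whether any adverse event occurred during application or since the last visit, without naming pain or burning.
- *Subject diary (Protocol 7.2.1, SAP 13.2.5).* It holds free complaints, which are listed.

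Several routes could therefore capture an application-time reaction, but only item 10 asks about it by name.

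**Reach of the problem**
The Protocol synopsis limits all endpoints other than the primary to descriptive, exploratory analysis. The item does not enter the primary analysis, the significance level or the sample size.

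**The case against.** The strongest reply is that application-time reactions are not lost. The investigator applies the adhesive, holds the wound and can record an adverse event, a complaint or a complication the same day, and SAP 12.3 summarises adverse events during application. That stands: a reader might infer that the event goes unrecorded unless item 10 catches it, and the documents do not support this. What remains is that none of these routes puts a specific question, and mild transient sensations are what unprompted recording tends to miss.

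A second reply concerns size, and it also stands. A reader might take the 6.1% for pain in Protocol Section 5, multiply by 189 subjects to get 0.061 × 189 = 11.5 events, and assume that some fraction is forgotten. Section 5 reports rates seen with other skin adhesives and does not tie them to the moment of application. No recall-loss fraction appears anywhere in the documents.

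Third, a reader might infer that both products carry a stated risk of pain or burning at application. For MAR-CUTIS the documents only carry over the rates from other adhesives. For Dermabond Advanced, Protocol 7.4.5 says "the subject may experience an increased sensation of heat or discomfort", but only if a second layer is applied or large droplets are left unspread, and the Instructions for Use mention warmth. Burning appears only in connection with the questionnaire item.

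Finally, item 10 asks what the investigator observed, so a No for an anesthetized subject is literally correct. It is still hard to interpret, because Protocol 7.4.8 exempts intraoperative anesthesia from capture in the eCRF. The documents do not say how many subjects this concerns.

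**Conclusion.** The point holds as a minor one. Item 10 is answered 23 to 37 days after application, or at Early Discontinuation if earlier, by an unblinded investigator who by then knows the outcome. A Day 0 section of the same form could carry it at once. No other form asks specifically about pain or burning at application.

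The interval assumes that Month 1 means 30 days. How much is under-recorded, and whether the arms are affected differently, cannot be given: the documents contain no application-pain rate for either product. A claim that the between-arm comparison is biased by a given amount or in a given direction would go beyond them.

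I found no reason in either document for asking at Month 1. The item numbers jump from 3 to 8 between the first two sections, and Protocol 9.2 omits the item. Both would fit a drafting slip, but that is inference.

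**What to change.** Move item 10 from the Month 1 section to Section 1 of questionnaire 15.6, to be answered for both products once the adhesive has been applied. Align the description of the form in Protocol 9.2, the form itself in 15.6, and the timing in SAP 13.2.6. If Month 1 answers have already been collected, tabulate them separately from Day 0 answers.

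Optionally, add a response for subjects who could not be assessed because they were anesthetized, and report its count. Its possible reach is wide. Incisions number about 189 − 40 = 149 by the laceration target in Protocol 7.2.1, or 0.85 × 189 ≈ 161 by the 85% assumed in Protocol 10.2. How many of these subjects could not report is unknown.

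The cost is one relocated eCRF item and a small protocol amendment with the ethics approval that Protocol 13.1 requires. If enrolment has begun, the item will have two collection time points. No visit or procedure is added, and sample size and power do not change.

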#### Section 3 (to be completed only in case of intentional premature removal of the adhesive)

- 1) Premature, intentional removal of glue strip was:

- |   |     |    |
|---|-----|----|
| Painless for subject                      | Yes | No |
| Easy                                      | Yes | No |
| Quick                                     | Yes | No |
| Didn't cause any additional complications | Yes | No |

if any answered "no", please explain the issue below:

Please explain which technique you used to remove the adhesive:

Please provide reason(s) for the removal:

---

## 15.7 Subject-completed Questionnaire

### Questionnaire for Subjects

Your opinion is very important to us and will help us to improve the quality of the product. We therefore would like to ask you to complete the following questionnaire which assesses positives and negatives of the wound closing method that has been used. Your doctor should be able to provide any help needed to complete this questionnaire.

This questionnaire should take a few minutes to complete.

Thank you

[figure not shown]
---

#### Section 1 (to be completed at Day 10 visit)

[figure not shown]
##### 1. Wound pain

Please evaluate the pain you are **now** experiencing in the area of your wound by indicating on the 100-mm line scale below with “no pain” at the left end (0 mm) and “excruciating pain” at the right” end (100 mm).

My pain right now is:

Please evaluate the **average** pain you have experienced in the area of your wound within the last seven (7) days by indicating on the 100-mm line scale below with “no pain” at the left end (0 mm) and “excruciating pain” at the right end (100 mm).

**Section 2 (to be completed at Day 10 visit)**

**2. Practical Experience/Ease of Use**

1) You were given written instructions of how to take care of your wound after the surgery. Please answer the questions below by indicating 'yes' or 'no':

The instructions were easy to understand	Yes	No
The instructions were easy to implement	Yes	No

2) How did the wound affect your daily activities? Please complete the table below, based on what you experienced after your surgical procedure:

	Very inconvenient	A little bit inconvenient	Neither positive, nor negative	Convenient	Very convenient
Impact on your daily activities:					
During showering/washing					
When getting dressed and while wearing clothes					
During the day (moving, sitting, working)					
During the night (sleeping/lying in bed)					

3) How did you experience the application and changing of the wound dressing?

I did it myself	Yes	No
Easy/no problem	Yes	No

4) The glue strip of MAR-CUTIS is transparent when applied to the skin.

Did you find it useful?    Yes    No    Not applicable (had Dermabond)

5) Please indicate how the wound closure felt on your skin:

[figure not shown]
Comfortable	Yes	No
Tight (tension at the wound)	Yes	No
Itchy	Yes	No
Loose (as if falling off)	Yes	No

---

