### Treatment Phase

Use of Dermabond Advance will be according to Instructions for Use (Section 15.2). Wounds closed with Dermabond Advanced will be prepared in a standard manner. They will be cleaned with an antiseptic solution (which will be recorded in the eCRF), patted dry with dry, sterile gauze, and hemostasis will need to be achieved prior to wound closure (eg, by pressure application or use of local vasoconstrictors). Wound edges will be approximated by fingers of forceps and Dermabond Advanced will be applied in one continuous layer onto a dry wound through painting motions, taking care not to apply adhesive between the wound edges. Applying a second layer is not required or recommended. If a second layer of Dermabond Advanced is applied, or if large droplets of liquid are not spread thinly, the subject may experience an increased sensation of heat or discomfort. The wound will be held for 60 seconds to allow for complete polymerization. The wound may or may not be covered with a protective dressing thereafter.

Wounds closed with MAR-CUTIS will be prepared in a standard manner. They will be cleansed with an antiseptic solution (which will be recorded in the eCRF), patted dry with dry, sterile gauze, and hemostasis will need to be achieved prior to wound closure (eg, by pressure application or use of local vasoconstrictors). The use of peroxide-containing antiseptics is not recommended to be applied directly on the MAR-CUTIS strip as they may provoke cracking of the strip. These products however may be used for preparing the wound for closure. In addition, iodine-containing products may be used as necessary but they may stain the glue strip making it non-transparent. Wound edges will be approximated by fingers of forceps and MAR-CUTIS will be applied in one 1 to 2 mm thick layer ensuring that at least 1 cm of the glue is applied over the length of the wound on each side. The amount of the glue applied will be calculated such that one 5-mL syringe covers up to 8 cm of wound length (giving a total of 10 cm per syringe). For wounds >8 cm, 2 syringes will be needed. The wound will be held for approximately 30 seconds to allow for initial polymerization. Only for the pediatric population, the maximum number of syringes per day is limited based on the body weight as shown in the table below:

Body Weight	Number of MAR-CUTIS Syringes
10 to <15 kg	Maximum of 1 syringe
15 kg and above	Maximum of 2 syringes

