A protective dressing may be applied after 3 minutes and instructions will be given to the subject on wound protection and showering as MAR-CUTIS requires moisture protection during showering.

If necessary, further dressing and wound management will be performed in accordance with the local practice.

Evaluation of all wounds will occur on Day 1, Day 10, Month 1, and Month 3/Early Discontinuation.

All subjects (or subject legal guardians in case of a pediatric subject) will be issued a subject's diary to record any wound exposure to water and any complaints. The diaries will be collected at the Month 1 study visit and analyzed descriptively.

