8 ANALYSIS CONVENTIONS

8.1 General principles

If two of the analysis sets as defined in the SAP coincide, presentations will only be prepared for one analysis set.

All presentations will be done by treatment group and overall, and by visit where applicable.

The data collected and derived in the trial will be presented in subject data listings sorted by subject number and treatment.

Data collected in this trial will be summarized according to their nature as follows:

- Continuous variables: number of non-missing observations, arithmetic mean, standard deviation (SD), minimum (Min) and maximum (Max) values, median, and first (Q1) and third (Q3) quartiles. If there are less than 5 observations, descriptive statistics will be presented based on the rules specified in Section 16.1.1.2.
- Categorical variables: absolute and relative frequencies. If not defined otherwise, the percentage denominator will be the number of subjects still in the trial (including missing values) at the respective time point in the analysis set. The category missing will only be displayed if missing values occur. Categories with a frequency of 0 will not be presented if not otherwise specified.

Medical terms (e.g., prior and concomitant diseases, adverse events) will be coded via Medical Dictionary for Regulatory Activities (MedDRA) version 21.0 or latest version before the database is locked. For the analysis, the primary System Organ Class (SOC) will be used. Medications will be coded according to World Health Organization Drug Dictionary (WHO-DD) version March 2018 or latest version before the database is locked.

Shells for summary tables, subject listings, and figures are described in a separate document, which is included as an Appendix to the SAP. Templates for each unique table, listing, and figure are provided. These provide only a draft indication of the content and appearance of the tables, listings, and figures, and the final output may vary in appearance from these templates.

All statistical analyses will be performed using SAS statistical software version 9.4 or higher (SAS Institute, Cary, NC).

[Table 1](#) shows the use of analysis sets in different analyses as defined in Section 9.

Table 1: Use of analysis sets

	Enrolled Set	Allocated Set	SAF	FAS
Subject disposition	X	X		
Discontinuations			X	
Protocol deviations			X	
Demographics			X	X
Other baseline characteristics			X	X
Subject medical history			X	
Previous and concomitant medication			X	
Exposure			X	

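### Day 10 subject questionnaire, item 3: a Yes/No question on dressing changes is put to all subjects although a dressing is optional, so its percentage may be distorted in either direction

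*Protocol*

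**What the plan says.** The item is in the subject-completed questionnaire (Protocol Section 15.7, Section 2, item 3). It asks "How did you experience the application and changing of the wound dressing" and gives two lines to answer: whether the subject did it personally, and "Easy/no problem". Each line takes Yes or No. No filter question or skip instruction precedes it. Item 4, directly below, does offer a third answer, "Not applicable (had Dermabond".

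The Treatment Phase text in Protocol Section 7.2.1 makes a dressing optional in both arms:

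- Dermabond Advanced: "The wound may or may not be covered with a protective dressing thereafter".
- MAR-CUTIS: "A protective dressing may be applied after 3 minutes".
- Both arms, afterwards: "If necessary, further dressing and wound management will be performed in accordance with the local practice".

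SAP 13.2.5 summarises each question of the questionnaire descriptively and sets no rule for subjects without a dressing. The default in SAP 8.1 therefore applies: "the percentage denominator will be the number of subjects still in the trial (including missing values". SAP 8.1 also shows a missing category whenever values are missing, and results are presented by treatment group. Neither document says that dressing use is recorded for each subject.

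**The concern.** The item only has meaning for a subject who had a dressing, but it is put to everyone and tabulated over everyone. A subject with no dressing has three possible responses:

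- **No**, which will be read as difficulty with the dressing.
- **Yes**, because the response line also covers having had no problem.
- **Blank**, which stays in the denominator and lowers the percentage as much as a No does.

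The published figure then mixes ease among dressed wounds with the way undressed subjects happened to answer. It cannot be read as the first of these. If dressing use or answering also differs by arm, part of any difference between arms would be an artefact.

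The mixture is hard to undo later. A No from an undressed subject looks the same as a No from a dressed subject who had trouble. The companion line does not help: a Yes there implies a dressing, but a No can mean either that someone else changed it or that there was none.

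What is at stake is the interpretation of one item in a secondary endpoint on subject comfort.

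**Working it through.** The documents give no dressing rate and no expected ease rate, so there is no stated figure to reproduce. All inputs below are assumptions, chosen to show the range.

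**Notation**

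- e = true proportion of Yes on the ease line among dressed subjects, taken as equal in both arms, so the true difference is 0
- c = proportion of subjects with a dressing
- y = proportion of undressed subjects who tick Yes; the rest tick No or leave it blank, and both count in the denominator under SAP 8.1

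**Formula**

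Reported rate R = e × c + y × (1 − c).

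With the same e and y in both arms (M = MAR-CUTIS, D = Dermabond Advanced), R_M − R_D = (e − y) × (c_M − c_D).

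**Unequal dressing use: e = 90%, c_M = 90%, c_D = 70%**

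| y | MAR-CUTIS | Dermabond Advanced | False gap |
|---|---|---|---|
| 0 | 0.9 × 0.9 = 81% | 0.9 × 0.7 = 63% | +18 points |
| 0.5 | 81% + 0.5 × 10% = 86% | 63% + 0.5 × 30% = 78% | +8 points |
| 1 | 81% + 10% = 91% | 63% + 30% = 93% | −2 points |

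Reversing the dressing rates reverses each sign.

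**Sensitivity**

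- At y = 0 and the same 20-point difference in dressing use, e = 80% gives 0.80 × 0.20 = 16 points and e = 95% gives 0.95 × 0.20 = 19 points.
- With dressing use of 90% versus 50% and e = 90%, the gap is +36 points at y = 0 (81% versus 45%), +16 at y = 0.5 (86% versus 70%) and −4 at y = 1 (91% versus 95%).

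**Equal dressing use: c = 80% in both arms, e = 90%**

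The reported rate is 72% at y = 0, 82% at y = 0.5 and 92% at y = 1, the same in each arm. There is no false gap, but the level departs from 90% in either direction.

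**Unequal answering**

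If dressing use is equal but y differs by arm, the gap is (1 − c) × (y_M − y_D), which is not zero.

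**After the fix**

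With dressed subjects only in the denominator, R = e in each arm (90% versus 90%), and the gap is 0 whatever the dressing rates.

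**The case against.** The strongest reply is that a reader might infer more than the documents support, namely that undressed subjects are forced into No or blank, that the ease percentage must therefore fall, and that the comparison is biased between the arms.

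- **The rate need not fall.** The response line is "Easy/no problem", so a subject without a dressing can truthfully tick Yes. If undressed subjects tick Yes as often as dressed ones (y = e), there is no distortion; if more often, the rate rises. This stands, and it is why the point is one of distortion in either direction.
- **Blanks are visible.** SAP 8.1 shows the missing category, and SAP 16.1.1.2 requires the number and percentage for it. A reader could remove blanks from the denominator. This stands for blanks, but not for a No or a Yes ticked for want of a better option.
- **Unequal dressing use is not shown.** The protocol says that "MAR-CUTIS requires moisture protection during showering", and the Dermabond Advanced instructions (Protocol Section 15.2) allow gentle showering at once as the physician directs. That makes a difference plausible. However, moisture protection in the shower need not be a dressing, and the Dermabond Advanced instructions also restrict wetting and permit dry dressings. Center is a randomization factor, which should largely balance site habits between arms. It would not balance a choice made after allocation because of the product, which is possible in an open-label trial, but the documents give no evidence of such a choice.
- **The reach is small.** Each question is summarised separately with no composite score, and how the closure felt on the skin is asked in item 5. The item names the dressing, so a careful reader would not take it as a measure of the adhesive alone. This stands.

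**Conclusion.** The point holds as a minor form and denominator defect. As written, item 3 and the SAP default produce a percentage by arm that mixes applicable with inapplicable answers and cannot be interpreted as ease among dressed wounds.

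Its size is unknown. On the assumptions above (90% ease among dressed subjects, 90% versus 70% dressed) the false gap lies between +18 and −2 points, depending on how undressed subjects answer. The +18 is the extreme in which none of them ticks Yes and should not be quoted as an expected bias. A false difference between arms also requires unequal dressing use or unequal answering, which is plausible but not shown.

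The protocol synopsis makes all endpoints other than the primary descriptive and exploratory. The primary endpoint, its noninferiority test, the significance level, the power and the sample size are untouched.

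**What to change.** - **Form and eCRF:** add *Not applicable (no dressing used)* to item 3, in line with what item 4 already does.
- **SAP 13.2.5:** state that item 3 is summarised among subjects with a dressing, and that the number and share without a dressing are reported by arm.

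The cost is one answer box, the matching eCRF change and a line in the SAP. Wound care does not change.

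If forms are already in use, the answers collected so far cannot be separated from the form alone. The SAP and report should then state the limitation next to the result. If dressing use can be obtained from another record, the item should be shown for dressed subjects as well.
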